5.3. EP547

EP547 is a potent inverse agonist (low nM inhibitor) of MRGPRX4. In vitro studies have shown that EP547 antagonizes at least 18 MRGPRX4 agonists in several cell lines (overexpressing Chinese hamster ovary [CHO] and human embryonic kidney [HEK]-293 cells and in endogenously expressing SH-4 melanoma cells), utilizing an array of assay readouts (calcium mobilization, inositol phosphate-1 [IP-1] accumulation, and β -arrestin recruitment). In vivo absorption, distribution, metabolism, and excretion studies demonstrated that EP547 is highly bound to human plasma proteins, has high bioavailability with total volume of distribution similar to body water (approximately 0.8 L/kg), and biodistributes to sites of action in the skin and dorsal root ganglion. Pharmacokinetic (PK) studies in monkeys demonstrated that maximum (peak) plasma concentration (C_{max}) occurred approximately 2 hours after oral dosing with a half-life of approximately 18 hours. In vitro safety studies to date demonstrate no meaningful safety signals.

[REDACTED]

[REDACTED] Additional information for these studies is provided in the Investigator's Brochure.

In view of the available nonclinical data, further development of EP547 for the treatment of cholestatic or uremic pruritus is warranted. This first-in-human study is designed to assess the safety, tolerability, PK, and pharmacodynamics (PD) of single and multiple ascending doses of EP547 in healthy subjects and subjects with cholestatic or uremic pruritus. The outcome of EP-547-101 will inform the design of future clinical studies evaluating EP547.

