12.1. Blood Sampling for Pharmacokinetics

Blood sampling for PK of EP547 will be collected as follows:

- **SAD-HS, SD-CP, and SD-UP:** predose and at 0.25, 0.5, 1, 1.5, 2, 2.5, 3, 4, 6, 9, and 12 hours postdose on Day 1; 18, 24, and 36 hours postdose on Day 2; 48 hours postdose on Day 3; and at follow-up on Day 8.
- **MAD-HS:** predose and at 0.25, 0.5, 1, 1.5, 2, 2.5, 3, 4, 6, 9, 12, and 18 hours postdose relative to the dose of study drug on Day 1; predose on Day 2 through Day 6; predose and at 0.25, 0.5, 1, 1.5, 2, 2.5, 3, 4, 6, 9, 12, and 24 hours postdose relative to the last dose of study drug on Day 7; and at follow-up on Day 14 and Day 21.
- **MAD-CP:** predose and at 0.25, 0.5, 1, 1.5, 2, 2.5, 3, 4, 6, 9, 12, and 18 hours postdose relative to the dose of study drug on Day 1; predose on Day 2; predose on Day 4; predose and at 0.25, 0.5, 1, 1.5, 2, 2.5, 3, 4, 6, 9, 12, and 24 hours postdose relative to the last dose of study drug on Day 7; and at follow-up on Day 14 and Day 21.
- **MAD-UP:** predose and at 0.25, 0.5, 1, 1.5, 2, 2.5, 3, 4, 6, 9, 12, and 18 hours postdose relative to the dose of study drug on Days 1, 2, and 6; predose on Day 4; predose and at 0.25, 0.5, 1, 1.5, 2, 2.5, 3, 4, 6, 9, 12, and 24 hours postdose relative to the last dose of study drug on Day 7; and at follow-up on Day 14 and Day 21.

The MAD dosing and PK blood sampling schedule is summarized in [Appendix C](#). The assessment window for blood sample collection timepoints for the single and multiple dose segments is also included in [Appendix C](#).

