### 3.3 Inferential Analyses

Descriptive statistics will be used to summarize the safety and PK data. No formal hypothesis testing is planned. To further explore on the plasma PK data, dose proportionality will be assessed for SAD-HS and MAD-HS segments.

- Dose Proportionality

- SAD-HS

Dose proportionality will be assessed for  $C_{max}$ ,  $AUC_t$  and  $AUC_{0-inf}$  using the power model. An assessment of dose proportionality will not be based strictly on statistical rules criteria but rather, several factors will be considered when assessing dose proportionality, such as results derived from a Power Model (e.g., the slope estimate, and the width of the 90% confidence intervals [CIs]), graphical evaluation, and descriptive statistics by dose level.

Details are as follows:

- Power Model: The power model will be used to estimate the slope parameter and the 90% CIs for the slope. The general form of the power model is described as:

$$\ln(\text{PK Parameter}) = \beta_0 + \beta_1 \ln(\text{Dose}) + \varepsilon$$

This approach is usually referred to as a power model because after exponentiation:

$$\text{PK Parameter} = \alpha \text{Dose}^{\beta_1}$$

where  $\alpha$  only depends on  $\beta_0$  and  $\varepsilon$  and represents the y-intercept of the line and  $\beta_1$  represents the slope of the line.

Linear relationships between the log-transformed PK parameter and the log of the dose will be tested to obtain an estimate of the slope parameter ( $\beta_1$ ) and 90% confidence interval (CI) for the slope. Dose proportionality can generally be concluded if the 90% CI around the slope estimate (i.e.,  $\beta_1$ ) includes the value of 1.

- MAD-HS

- Similar model as explained above will be used to assess dose proportionality for the parameters  $C_{max}$ ,  $AUC_t$ ,  $AUC_{0-inf}$  and  $AUC_{\tau}$  calculated on Day 1 and Day 7 separately.

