$t_{1/2}$	
Apparent terminal half-life, using the following formula
 $T_{1/2} = \frac{\ln(2)}{\lambda_z}$
CL/F	
Apparent total plasma clearance, using the following formula
 $CL/F = \frac{D}{AUC_{0-\infty}}$ 
Where D = Administered dose; <math>AUC_{0-\infty} = AUC_{0-inf}</math>

$V_z/F$	
Apparent terminal volume of distribution, using the following formula
 $V_z/F = \frac{CL/F}{\lambda_z} \text{ Or } \frac{Dose}{\lambda_z \times AUC_{inf}}$
Corrected M/P ratio for $C_{max}$	
Corrected metabolite to parent ratio for <math>C_{max}</math> is calculated using the following formulae
 
(<math>C_{max}</math> metabolite/<math>C_{max}</math> parent) *(Molecular Weight of parent drug/Molecular Weight of metabolite)

Corrected M/P ratio for AUC 0-t	
Corrected metabolite to parent ratio for AUC0-t is calculated using the following formulae
 
(AUC0-t metabolite/ AUC0-t parent) *(Molecular Weight of parent drug/Molecular Weight of metabolite)

**Plasma Pharmacokinetic Parameters at steady state on pre-defined days following multiple dose administration for the MAD-HS and MAD-CP segments (Day 1 and Day 7) and for the MAD-UP segment (Day 1, Day 2, Day 6, and Day 7)**

Parameter	Definition
C max	Maximum steady state concentration time over the dosing interval
C trough	The pre-dose trough concentration observed at the last planned timepoint prior to next dosing
T max	Time to reach maximum concentration over the dosing interval. If the same C max concentration occurs at different time points, T max is assigned to the first occurrence of C max .
AUC 0-t	Area under the drug concentration-time curve, from time zero to the last measurable concentration using the 'Linear Up and Log Down' method
AUC 0-τ	Area under the plasma concentration-time curve over a dosing interval using the 'Linear Up and Log Down' method
AUC 0-24hr	Area under the drug concentration-time curve, from time zero (time of dosing) to 24 hours post-dose using the 'linear Up and Log Down' method
AUC 0-48hr	Area under the drug concentration-time curve, from time zero (time of dosing) to 48 hours post-dose using the 'linear Up and Log Down' method

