#### 10.1.1.2 Goodness of Fit

- If data permits, the default 'best fit' method by Phoenix WinNonlin will be used for the selection of slopes to determine ' $\lambda_z$ '. If data do not permit, then the slope selection will be done by visual inspection or by a manual method to determine  $\lambda_z$ .
- When assessing terminal elimination phases, the adjusted  $R^2$  value will be used as a measure of the goodness of fit of the data points to the determined line.
- Regression-based parameters ( $\lambda_z$ , AUC0-inf,  $t_{1/2}$ , CL/F or CL/Fss, and  $V_z/F$  or  $V_z/F_{ss}$ ) will only be calculated if the adjusted  $R^2$  value of the regression line is greater than or equal to 0.8 and AUC%extrap is  $<20\%$ . If regression-based parameters cannot be calculated, they will be set to "NC", defined as "not calculable" in the data listings and summary tables as appropriate.

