## 10.4 Pharmacokinetic Noncompartmental Analysis (NCA)

### 10.4.1 General Plasma NCA Pharmacokinetic Settings

The general settings in Phoenix WinNonlin® for generation of plasma PK parameters are as listed below.

- NCA Model Type Plasma (200-202)
- Weighting Uniform
- AUC Calculation Method: Linear Up/Log Down
- Dose Options Type Extravascular
- Slopes Setting Fit Method: Best Fit
- Rsq\_Adjusted Criteria for 'λz' 0.8
- AUC% extrapolation Criteria 20

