### 10.4.3 Inferential Analyses

For SAD-HS and MAD-HS, the following endpoints will be analyzed as described in section 3.3:

- Dose proportionality:
  - $C_{\text{trough}}$  (Only Day 7 value to be used to assess DP for MAD )
  - $C_{\text{max}}$
  - $AUC_{0-t}$
  - $AUC_{0-\text{inf}}$
  - $AUC_{0-\tau}$  (as appropriate, MAD only)

Dose proportionality will be assessed graphically ( $C_{\text{max}}$ ,  $AUC_{0-t}$  and  $AUC_{0-\text{inf}}$  versus dose) on log scale for both axes. PK parameters derived from Day 1 (SAD & MAD) and Day 7 (MAD) will be subjected to dose proportionality assessment for entire dose range studied for EP-547-101. From each model, the slope of the regression line  $\beta$  will be presented along with the 90% CI of the slope. The regression line formulae along with correlation coefficient ( $r^2$ ) will be presented in the plot.

Sample SAS Code for dose-proportionality analysis using power model. Programmers will need to modify as appropriate to the study:

```
proc mixed;  
  by PKParameter;  
  model lnPKParameter = lnDose / cl alpha=0.1 solution ddfm=kr;  
run;
```

For FE-HS, the following endpoints will be analyzed as described in section 3.3:

- Food Effect analysis:

- o  $C_{\max}$
- o  $AUC_{0-t}$
- o  $AUC_{0-\infty}$
- o  $T_{\max}$

[REDACTED]

- [REDACTED]
- [REDACTED]
- [REDACTED]
- [REDACTED]
- [REDACTED]
- [REDACTED]
- [REDACTED]
- [REDACTED]

[REDACTED]

- [REDACTED]
- [REDACTED]
- [REDACTED]

**11.1** [REDACTED]

[REDACTED]

**11.2** [REDACTED]

[REDACTED]

**11.3** [REDACTED]

[REDACTED]

- [REDACTED]
- [REDACTED]
- [REDACTED]
- [REDACTED]
- [REDACTED]
- [REDACTED]
- [REDACTED]
- [REDACTED]
- [REDACTED]

[REDACTED]

[REDACTED]

[REDACTED]

[REDACTED]

[REDACTED]

[REDACTED]

[REDACTED]

[REDACTED]

[REDACTED]

[REDACTED]

[REDACTED]

[REDACTED]

[REDACTED]

[REDACTED]

[REDACTED]

[REDACTED]

[REDACTED]

[REDACTED]

[REDACTED]

[REDACTED]

[REDACTED]

**11.7** [REDACTED]

[REDACTED]

[REDACTED]

[REDACTED]

[REDACTED]

[REDACTED]

[REDACTED]

[REDACTED]

[REDACTED]

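### AUC0-inf does not belong in the MAD-HS dose-proportionality model: it is undefined on Day 7, and on Day 1 the SAP's own 20% limit would remove most values if the human half-life exceeds about 10 h

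*SAP*

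**What the plan says.** - **What is modelled.** SAP 3.3 applies the power model for MAD-HS to Cmax, AUCt, AUC0-inf and AUCtau, "calculated on Day 1 and Day 7 separately". SAP 10.4.3 repeats the list and adds that "PK parameters derived from Day 1 (SAD & MAD) and Day 7 (MAD) will be subjected to dose proportionality assessment". It marks AUC0-tau as MAD only but puts no segment limit on AUC0-inf, and it includes AUC0-inf in the log-log plots.
- **Where AUC0-inf is defined.** SAP 10.1 defines it in the Day 1 single-dose table, which covers SAD and MAD. The other MAD table, headed "Plasma Pharmacokinetic Parameters at steady state on pre-defined days following multiple dose administration", covers Day 7. It lists AUC0-t, AUC0-tau, AUC0-24hr and AUC0-48hr, but neither AUC0-inf nor the extrapolated percentage.
- **The limit.** SAP 10.4.1 sets "AUC% extrapolation Criteria 20". SAP 10.1.1.2 requires an extrapolated share below 20% and an adjusted R² of at least 0.8, and continues: "If regression-based parameters cannot be calculated, they will be set to" NC. SAP 3.5 then treats NC as missing.
- **Sampling.** Protocol 12.1 gives MAD-HS samples to 18 h after the first dose and then "predose on Day 2 through Day 6". Appendix C places the Day 2 predose sample less than 30 minutes before dose 2.
- **Half-life.** Protocol 5.3 gives monkey data only: the peak "occurred approximately 2 hours after oral dosing", "with a half-life of approximately 18 hours".
- **Protocol on parameters.** The MAD lists in Protocol 15.2.2 and 15.5 omit AUC-infinity. The power-model sentence in 15.5 names it without a segment.

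**The concern.** The plan asks for a model of a parameter that its own Day 7 table does not contain. On Day 1 the parameter is defined, but a 24 h profile may be too short to pass the extrapolation limit. Whether a value passes depends on the subject's half-life, so any loss is selective: subjects with short half-lives, and hence low exposure, are the ones kept.

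At stake are a Day 7 row carrying the wrong label, and a Day 1 row that is empty or rests on a few selected subjects. SAP 3.3 says proportionality can generally be concluded when the 90% CI for the slope includes 1. An interval widened by lost subjects includes 1 more easily.

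**Working it through.** The plan states no human half-life, no expected number of calculable AUC0-inf values and no power, so there is no planned figure on this point to reproduce.

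**Inputs from the documents.** Last Day 1 sample at about 24 h; limit 20%; 18 EP547 subjects in MAD-HS (3 levels × 6) at 25, 75 and 225 mg (Addendum, section 5).

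**Assumptions.** Log-linear decline; log-normal half-life with CV 30% to 50%; median half-life 8, 12 or 18 h.

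**1. Half-life at which the limit fails.** The extrapolated share at 24 h is 2^(−24/t½). It is below 0.20 only if t½ < 24 × ln 2 / ln 5 = 10.3 h. A one-compartment oral model with a 2 h peak gives 10.1 h. At 18 h the share is 2^(−24/18) = 0.397, about twice the limit. SAD-HS samples to 48 h, where the share at 18 h is 2^(−48/18) = 0.157, so AUC0-inf passes there.

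**2. Subjects left on Day 1.** With σ = √ln(1 + CV²), which is 0.294 at 30% and 0.472 at 50%, the chance of passing is p = Φ(ln(10.34/median)/σ), and the expected number is 18p.

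| Median t½ | p, CV 30% | Left of 18 | p, CV 50% | Left of 18 |
|---|---|---|---|---|
| 18 h | 0.029 | 0.5 | 0.120 | 2.2 |
| 12 h | 0.306 | 5.5 | 0.376 | 6.8 |
| 8 h | 0.809 | 14.6 | 0.706 | 12.7 |

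The oral threshold of 10.1 h gives slightly fewer (0.4 to 2.0 at 18 h).

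**3. Can a slope be fitted?** At least two dose levels must keep a value. With q = (1 − p)^6, the chance that they do not is q³ + 3q²(1 − q). At 18 h this is 0.93 for CV 30% (q = 0.836) and 0.45 for CV 50% (q = 0.464). A confidence interval also needs at least three values; it is unavailable in about 98% to 99% of trials at CV 30% and 65% at CV 50%.

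**4. Effect on the estimate** (simulation: 3 doses × 6, median 12 h, half-life CV 30%, volume CV 15%).

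- Half-life the same at every dose: the mean slope after exclusion is 1.00. The geometric mean AUC0-inf of those kept is about 29% low, and the median 90% CI half-width grows from 0.147 to 0.213.
- Half-life rising as dose^0.2, so the true slope is 1.20: the mean slope after exclusion is about 1.06. The interval includes 1 in about 89% of trials that yield one, against roughly 30% with no exclusion and somewhat over 40% for Day 1 AUC0-tau.

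**5. Day 7.** With r = 2^(−24/t½), the AUC from dose 7 to infinity divided by the single-dose AUC0-inf is (1 − r^7)/(1 − r). This is 1.33, 1.66 and 1.98 at 12, 18 and 24 h. By contrast, Day 7 AUC0-tau equals (1 − r^7) times the single-dose AUC0-inf: 0.998 at 18 h (r = 0.397) and 0.992 at 24 h (r = 0.5). Under linear kinetics, AUC0-tau on Day 7 therefore already measures what AUC0-inf was meant to capture.

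**The case against.** Several points on the other side stand.

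- **The Day 1 loss is conditional.** A reader might infer that the limit will remove most MAD-HS subjects. The documents do not support that as a fact, because they give no human half-life. At 8 h most subjects remain.
- **The slope is not necessarily biased.** A reader might take the 1.33 to 1.98 factors, or the 29% shortfall, as errors in the dose-proportionality result. If half-life does not change with dose, both are the same at every dose level: they move the intercept and leave the slope alone. Bias needs a half-life that changes with dose, and nothing in the documents shows that it does.
- **The protocol does not exclude the parameter.** A reader might infer that the SAP contradicts the protocol's MAD list. That list is expressly not exhaustive, and the protocol's power-model sentence names AUC-infinity without a segment. SAP 10.1 also allows additional parameters. None of these supplies a Day 7 definition.
- **The plan partly copes already.** Values that fail become NC, and Cmax, AUC0-t and AUC0-tau are modelled on both days. SAP 3.3 plans no hypothesis test and does not rest proportionality on the interval alone.

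These points limit the consequence. They do not give Day 7 AUC0-inf a meaning, and handling failures as NC does not undo the selection among the values that remain.

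**Conclusion.** The Day 7 defect holds whatever the half-life: the SAP calls for a model of a parameter that its steady-state table does not define, and the Day 1 formula would give a mislabelled quantity. The Day 1 defect holds if the human half-life is above about 10 h. At the only documented value, about 18 h in monkeys, nearly all AUC0-inf values would be lost for any half-life CV from 30% to 50%. At 8 h roughly 13 to 15 of 18 would be kept.

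The slope is unbiased when half-life is constant across doses. When half-life rises with dose, the exclusion pulls the slope toward 1, and the wider interval makes proportionality easier to conclude. The sizes rest on log-linear decline, log-normal half-lives and the assumed CVs. Severity is low to moderate: the analysis is exploratory and three other parameters remain. The 20% limit itself is not in question.

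**What to change.** - In SAP 3.3 and 10.4.3, including the log-log plots, restrict AUC0-inf to SAD-HS.
- Name AUC0-tau, already listed, as the MAD-HS extent-of-exposure parameter on Day 1 and Day 7. It needs no extrapolation to infinity, so all 18 subjects with complete sampling can contribute. The Day 1 interval may close up to 30 minutes early, which a line on handling the predose sample would cover.
- Where AUC0-inf is still summarised for MAD Day 1 (Table 14.2.2b), show the number calculable at each dose and footnote that subjects with shorter half-lives are more likely to be included.

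The cost is SAP wording, one fewer row in the MAD-HS dose-proportionality output for each day, and a count with a footnote in one table. No further data are needed.

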### Food Effect Analysis

- FE Segment

The effect of food will be assessed for  $AUC_{\infty}$ ,  $AUC_{0-t}$ ,  $C_{max}$  using mixed effect model.

A mixed effect model will be fitted separately to each of the log transformed PK parameters with period and treatment (fed or fasted) as fixed effects and subject as a random effect. Model assumptions will be checked and appropriate adjustments may be applied to the data. Point estimates for the differences in means (EP547 fed – EP547 fasted) and corresponding 90% confidence intervals (CIs) will be constructed from the least-squares means, using the residual variance. These will then be back-transformed to provide point estimates and corresponding 90% CIs for the ratio of geometric means fed:fasted. Intra-subject coefficient from the model will also be presented.

The effect of food on  $T_{max}$  will be analyzed nonparametrically using the Wilcoxon signed-rank test to compute the point estimate and 90% CI for the median difference (EP547 fed – EP547 fasted). This endpoint will not be log transformed for analysis.

### 3.4 Multiple Comparisons and Multiplicity Adjustments.

Not applicable for this study.

### 3.5 Handling of Missing Data

For the classification of Treatment emergent adverse event (TEAE) and Concomitant medication, the following will be applied in the following order:

- a. If all dates/times (start and stop) missing, the event/medication will automatically be classified as a TEAE/Concomitant medication.
- b. For adverse events (AEs) with a missing start date/time, if the event end date/time is prior to first study drug administration, the event will not be classified as a TEAE.
- c. If only the AE start year/ medication end year is present and is the same or is after the first study drug administration year unit, the event/medication will be classified as a TEAE/Concomitant medication.
- d. If the AE start month and year/medication end month and year are present and are the same or after the first study drug administration month and year units, the event/medication will be classified as a TEAE/Concomitant medication.

For the PK analysis the following will be applied:

- a. For the concentration descriptive summaries, concentrations may be excluded if sampling time deviation is considered large to affect the profile at the discretion of the pharmacokineticist.
- b. Concentrations (plasma and skin) that are below limit of quantification (BLQ which is 10 ng/mL undiluted) prior to the first quantifiable value will be set equal to zero. Post dose BLQ concentrations will be set to missing.
- c. Where there are no results (NR), these will be set to missing.
- d. If more than 75% of values per nominal timepoint and treatment group are BLQ, then all descriptive statistics, except for nBLQ, will be denoted as not calculable (NC).
- e. For the calculation and graphical representation (semi-log and log-log plots) of geometric descriptive statistics, 0 values will be set to missing.
- f. For the purpose of calculating the non-compartmental PK parameters, plasma concentrations that are BLQ prior to the first quantifiable value will be set equal to zero. BLQ values after measurable concentrations will be set to missing.
- g. For the calculation of summary statistics of PK parameters, all NR and NC values in a data series will be set to missing.

#### Conversion of categorical values

In some instances, continuous variables are expressed as a range (i.e. < 10). In such cases, values may be converted to the range boundary (upper or lower limit as applicable). As an example, a value of <10 may be converted to 10. Such substitutions will be clearly documented in the footnotes of relevant outputs.

### 3.6 Coding of Events and Medications

Medical history and AE verbatim terms will be coded using the Medical Dictionary for Regulatory Activities (MedDRA), version 23.0. Terms will be coded to the full MedDRA hierarchy, but the system organ class (SOC) and preferred terms (PT) will be of primary interest for the analysis.

Prior and concomitant medications will be coded using the World Health Organization Drug Dictionary, version March 2020. Medications will be mapped to the full WHO-DD Anatomical Therapeutic Chemical (ATC) class hierarchy, but PTs will be of primary interest in this analysis.

### 3.7 Treatment Groups/Treatment Sequence

#### 3.7.1 Baseline Characteristic, Demography, Safety and PD outputs

For listings, all segment data will be presented together in one listing as per segment and dose level (available) with the following treatment group labels:

- Group 1: SAD HS/ EP547 25 mg
- Group 2: SAD HS/ EP547 75 mg
- Group 3: SAD HS/ EP547 225 mg
- Group 4: SAD HS/ EP547 450 mg
- Group 5: SAD HS/ EP547 TBD mg
- Group 6: MAD HS/ EP547 25 mg QD
- Group 7: MAD HS/ EP547 75 mg QD
- Group 8: MAD HS/ EP547 TBD mg QD
- Group 9: SD CP/ EP547 TBD mg
- Group 10: SD UP/ EP547 TBD mg
- Group 11: MAD CP/ EP547 TBD mg QD
- Group 12: MAD CP/ EP547 TBD mg QD (optional)
- Group 13: MAD UP/ EP547 TBD mg QD
- Group 14: MAD UP/ EP547 TBD mg QD (optional)

For summary, separate tables will be provided for each segment (SAD-HS, MAD-HS, SD-CP/SD-UP, MAD-CP/MAD-UP) with the following treatment group labels:

